3.1 Selection of Patients

The target population for this study is patients with stage IV breast, NSCLC lung cancers and Sarcoma.

This will be a multi-center trial conducted by Mays Cancer Center. At Mays Cancer Center, patients will be recruited by the clinical team in the Breast Center; lung center and sarcoma center. Potential patients may be referred to the Principal Investigator, [name], at [contact].

Eligibility will be evaluated by the study team according to the following criteria. Eligibility waivers are not permitted. Subjects must meet all of the inclusion and none of the exclusion criteria to be registered to the study. Study treatment may not begin until a subject is registered. Please refer to Section 11 for complete instructions regarding registration procedures.

Inclusion Criteria

- Stage IV breast cancer, stage IV NSCLC, stage IV sarcoma
- ECOG PS 0-2
- Measurable disease
- No more than 4 prior chemotherapeutic regimens for metastatic disease
- Patients must be \geq 18 years.
- Patients may not have received Eribulin or lenvatinib previously
- Patients must have a life expectancy of greater than 12 weeks.
- Patients may have had a prior diagnosis of cancer if it has been $>$ 5 years since their last treatment and are considered free of disease.
- Patients must have normal organ and marrow function as defined below:
 - Leukocytes \geq 3,000/ μ L
 - Absolute neutrophil count \geq 1,500/ μ L
 - Platelets \geq 100,000/ μ L
 - Child Pugh score \leq 10
- Patients must be able to swallow and retain oral medication.
- All patients must have given signed, informed consent prior to registration on study.

Exclusion Criteria

- Women who are pregnant or lactating are not eligible for study treatment.
- Patients who are undergoing concomitant radiotherapy are NOT eligible for participation.
- Patients who are receiving any other investigational agents or concurrent anticancer therapy are NOT eligible for participation. Previous systemic treatment and/or radiation therapy is allowed with a 14 day washout period prior to registration.
- Lesions that have been radiated previously cannot be considered target lesions
- Prior treatment related side effects must have resolved to $<$ Grade 2 severity per Common Terminology Criteria for Adverse Events (CTCAE version 4.03), except alopecia and infertility.

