4.2 Study Drug Administration

Eribulin

Eribulin will be administered intravenously (IV) on days 1 and 8 of each cycle at a dose of 1.4 mg/m² over a 2-5 minute time period; on cycle day 1 in the Phase II portion of the trial; this will be immediately prior to Lenvatinib administration. Eribulin will be administered to the patient in the clinic (for drug preparation instructions, see section 7.0). Each cycle will last 21 (+/- 3) days. Laboratory tests will be performed within 2 days prior to days 1 and 8 of all cycles to assess toxicity and confirm that it is safe to proceed with treatment (see Section 7.0 for a complete listing of assessments). The dose of Eribulin will be calculated based on the BSA at study entry and *should only be recalculated if there is >10% change in body weight from baseline*. The actual body weight will be used for these calculations.

Lenvatinib

Lenvatinib will be self-administered by patients orally once a day during the study period. Patients will self-administer lenvatinib at home, except on study visit days. On these visit days, patients should take lenvatinib after chemotherapy is administered. Patients will be instructed to take each dose orally once daily, with or without food, starting on day 2 of cycle 1. The capsules should be swallowed whole without chewing, dissolving, or opening them. Patients should be instructed to take their dose of study drug at the same time each day. If the usual dosing time is missed, the patient should take the dose that day as soon as they remember as long as this is within 12 hours of the usual time the patient takes the dose. If it has been over 12 hours then this will be considered a missed dose. Patients should not make up missed or vomited doses; dosing should resume on the next calendar day unless otherwise instructed. Patients will be given a medication diary to record all doses taken, missed/skipped, or vomited. This diary will be reviewed with study personnel prior to dispensing medication for the next cycle.

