4.7 Duration of Therapy

Patients may continue on study therapy until disease progression or until unacceptable toxicity occurs.

Patients will go off study therapy if any of the following occurs:

- The patient experiences any grade 4 toxicity after 2 dose modifications, as recommended by the protocol. If treatment is held for 2 consecutive treatment cycles due to toxicity, the patient must go off treatment.
- The patient withdraws consent from treatment or from the study as a whole.
- There is disease progression.
- The treating physician feels it is necessary (e.g. due to patient non-compliance or other safety concerns).

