5.2 Guidelines for Evaluation of Measureable Disease

All measurements should be taken and recorded in metric notation using a ruler or calipers. All baseline evaluations should be performed as closely as possible to the beginning of treatment and never more than 4 weeks before the beginning of the treatment.

The same method of assessment and the same technique should be used to characterize each identified and reported lesion at baseline and during follow-up. Imaging-based evaluation is preferred to evaluation by clinical examination when both methods have been used to assess the antitumor effect of a treatment.

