6.0 Study Parameters

Procedures	Screening & Baseline	Cycle 1	Every cycle ²	Every 2 cycles or at study termination	End of study visit ⁷	Follow-Up ⁶
Tissue procurement ¹	X			X ⁵		
Informed consent	X					
Eribulin administration			X (Days 1 & 8)			
Lenvatinib			X once daily (starting on day 2 of cycle 1)			
Medical history ³	X		X		X	
Physical exam ³	X		X		X	
CBC w/ diff	X ³		X		X	
Comprehensive chemistry panel	X ³		X			
TSH	X		X			
Serum pregnancy test	X					
EKG	X		X ¹⁰			
Blood draw for micro RNA assay ⁹		X			X	

Procedures	Screening & Baseline	Cycle 1	Every cycle ²	Every 2 cycles or at study termination	End of study visit ⁷	Follow-Up ⁶
Urine analysis ¹¹	X			X		
Imaging ⁸	X ⁴			X		
Toxicity assessment			X			
Biopsy				X ⁵		
Survival status						X

¹Archival tissue or a fresh biopsy will be required to procure tissue for study purposes. Biopsy does not need to be repeated for study purposes if archived tissue is available.

Tissue procurement is voluntary

²A cycle is defined as 3 weeks or 21 days (+/- 3 days). Eribulin will be given on cycle days 1 and 8 and lenvatinib starting on day 2 of cycle one and then continuously.

³Pre-study laboratory tests, medical history, and physical exam (including performance status and review of systems) must be completed within 28 days prior to registration.

Pre-study CBC and CCP will be repeated on day 1 prior to treatment administration.

⁴Pre-study imaging must be performed within 28 days prior to registration.

⁵At the initiation and completion of study treatment (or at the time of early withdrawal), tissue samples should be obtained for correlative studies. This is voluntary and will only be done on patients who consent to it.

⁶Patients will be followed every 6 months, at the time of routine clinic visit or via phone, until death, to document disease progression and survival.

⁷Within 30 days of last dose of study medications.

⁸Imaging modality is left to the discretion of the investigator. However the same imaging modality should be used every two cycles to assess disease status.

⁹Blood samples for microRNA assay will be collected on Cycle 1, Day 1 and at the end of treatment.

¹⁰Repeat EKG with every cycle in patients with congestive heart failure, bradyarrhythmias, or those who are taking drugs known to prolong the QT interval, including Class Ia and III antiarrhythmics.

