7.2 Lenvatinib

Other names

Lenvima

Classification

LENVIMA, a kinase inhibitor, is the mesylate salt of lenvatinib. Its chemical name is 4-[3-chloro-4-(*N*¹-cyclopropylureido)phenoxy]-7-methoxyquinoline-6-carboxamidemethanesulfonate.

Mode of action

Lenvatinib is a receptor tyrosine kinase (RTK) inhibitor that inhibits the kinase activities of vascular endothelial growth factor (VEGF) receptors VEGFR1 (FLT1), VEGFR2 (KDR), and VEGFR3 (FLT4). Lenvatinib also inhibits other RTKs that have been implicated in pathogenic angiogenesis, tumor growth, and cancer progression in addition to their normal cellular functions, including fibroblast growth factor (FGF) receptors FGFR1, 2, 3, and 4; the platelet derived growth factor receptor alpha (PDGFR α), KIT, and RET.

Storage and Stability

Store at 25°C (77°F); excursions permitted to 15–30°C (59–86°F)

Protocol dose

Lenvatinib is administered at a dose of 20 mg orally.

Preparation

LENVIMA 4 mg capsules are supplied as hard hyperomellose capsules with yellowish-red body and yellowish-red cap, marked in black ink with “€” on the cap and “LENV 4 mg” on the body.

LENVIMA 10 mg capsules are supplied as hard hyperomellose capsules with yellow body and yellowish-red cap, marked in black ink with “€” on the cap and “LENV 10 mg” on the body.

Protocol administration

Lenvatinib is administered orally 20 mg po daily. It will be administered immediately after the Eribulin administration.

Incompatibilities

None

Availability

Lenvima will be supplied by Eisai, Inc in cards containing 10 mg and 4 mg capsules. To order drug, please contact EISAI IIS Department at [contact] or [contact]

Side effects

Detailed information regarding side effects and rates of adverse events of lenvatinib can be found in the package insert. Some of the most common side effects include:

Hypertension

The median time to onset of new or worsening hypertension was 16 days for LENVIMA-treated patients. The incidence of Grade 3 hypertension was 44% as compared to 4% for placebo, and the incidence of Grade 4 hypertension was less than 1% in LENVIMA-treated patients and none in the placebo group.

Cardiac dysfunction

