8 USE IN SPECIFIC POPULATIONS

8.1 Pregnancy

Risk Summary

Based on its mechanism of action and data from animal reproduction studies, LENVIMA can cause fetal harm when administered to a pregnant woman [see *Clinical Pharmacology (12.1)*]. In animal reproduction studies, oral administration of lenvatinib during organogenesis at doses below the recommended human dose resulted in embryotoxicity, fetotoxicity, and teratogenicity in rats and rabbits [see *Data*]. There are no available human data informing the drug-associated risk. Advise pregnant women of the potential risk to a fetus.

The background risk of major birth defects and miscarriage for the indicated population is unknown; however, the background risk in the U.S. general population of major birth defects is 2-4% and of miscarriage is 15-20% of clinically recognized pregnancies.

Data

Animal Data

In an embryofetal development study, daily oral administration of lenvatinib mesylate at doses greater than or equal to 0.3 mg/kg [approximately 0.14 times the recommended human dose based on body surface area (BSA)] to pregnant rats during organogenesis resulted in dose-related decreases in mean fetal body weight, delayed fetal ossifications, and dose-related increases in fetal external (parietal edema and tail abnormalities), visceral, and skeletal anomalies. Greater than 80% postimplantation loss was observed at 1.0 mg/kg/day (approximately 0.5 times the recommended human dose based on BSA).

Daily oral administration of lenvatinib mesylate to pregnant rabbits during organogenesis resulted in fetal external (short tail), visceral (retroesophageal subclavian artery), and skeletal anomalies at doses greater than or equal to 0.03 mg/kg (approximately 0.03 times the human dose of 24 mg based on body surface area). At the 0.03 mg/kg dose, increased post-implantation loss, including 1 fetal death, was also observed. Lenvatinib was abortifacient in rabbits, resulting in late abortions in approximately one-third of the rabbits treated at a dose level of 0.5 mg/kg/day (approximately 0.5 times the recommended clinical dose of 24 mg based on BSA).

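### The serum pregnancy test is scheduled only at Screening & Baseline (6.0): none is required on day 1 before the first dose or during open-ended treatment

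*Combined protocol and SAP*

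**What the plan says.** Section 3.1 sets the bar: "Women who are pregnant or lactating are not eligible for study treatment".

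The 6.0 calendar has one mark in the serum pregnancy test row, under Screening & Baseline. The cells for Cycle 1, every cycle, every 2 cycles, end of study and follow-up are empty, and the row carries no footnote. The blood tests marked for every cycle are CBC, chemistry panel and TSH.

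Footnote 3 to the calendar gives pre-study laboratory tests a window of 28 days before registration, then adds: "Pre-study CBC and CCP will be repeated on day 1 prior to treatment administration". Its superscript sits on medical history, physical exam, CBC and chemistry panel.

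Section 5.2, under measurable disease, says: "All baseline evaluations should be performed as closely as possible to the beginning of treatment and never more than 4 weeks before" treatment begins.

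Section 4.2 says: "Laboratory tests will be performed within 2 days prior to days 1 and 8 of all cycles", in order to assess toxicity and confirm that treatment is safe. It does not name a pregnancy test. Section 4.7 says: "Patients may continue on study therapy until disease progression or until unacceptable toxicity occurs".

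For registration, 11.1.2 (safety run-in) lists a negative serum pregnancy test, if applicable, among the source documents. Section 11.1.3 (phase II) lists an eligibility checklist, consent and pathology report, with no separate pregnancy result.

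The lenvatinib label text in Appendix I (5.13, 8.1, 8.3) says that the drug can cause fetal harm and advises effective contraception during treatment and for at least 2 weeks afterwards. On human risk it says: "There are no available human data informing the drug-associated risk".

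**The concern.** The exclusion in 3.1 concerns treatment, but the only scheduled test that supports it is tied to screening. A woman who conceives between screening and day 1, or during therapy, would not be found by any scheduled test. Section 12.0 expects the study to be run as written, so a site in full compliance could start or continue both drugs in her.

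What is at stake is patient and fetal safety. The harm would be irreversible, and the animal harm in Appendix I followed exposure during organogenesis, so early detection matters. Eligibility starts at age 18 and includes breast cancer, NSCLC and sarcoma, so women of reproductive potential can enrol.

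**Working it through.** The plan gives no figure on this point to reproduce. The check is a reading of the schedule, followed by the age of the only test result.

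**1. Is there any test at or after first dose?**

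- 6.0 calendar: no mark after Screening & Baseline.
- 6.0 footnote 3: the day 1 repeat covers CBC and the chemistry panel only.
- 4.2: laboratory tests before days 1 and 8 are for toxicity. The calendar leaves the pregnancy cells empty, so these tests cannot fairly be read to include one.
- 5.2: at most a limit on how old a baseline evaluation may be; it adds no test.
- 11.1.2 and 11.1.3: both precede registration.

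The answer is no. Two cycles contain 2 × 2 = 4 scheduled pre-dose laboratory checks (days 1 and 8) and 0 pregnancy tests.

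**2. How old can the only result be?**

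Inputs:
- w = 28 days, from footnote 3 (counted back from registration) or from 5.2 (4 weeks, counted back from treatment).
- g = days from registration to first dose. The documents do not state it; 0 to 14 is assumed. If 5.2 caps the test, g drops out and is set to 0.
- L = cycle length, 21 ± 3 days (4.2 and 6.0 footnote 2), so 24 at most.

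Formulas: age at first dose = w + g; age after two cycles = w + g + 2L.

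| Reading | At first dose | After 2 cycles, L = 21 | After 2 cycles, L = 24 |
|---|---|---|---|
| 5.2 caps the test, or footnote 3 applies with g = 0 | 28 | 28 + 42 = 70 | 28 + 48 = 76 |
| Footnote 3 applies, g = 14 (assumed) | 28 + 14 = 42 | 42 + 42 = 84 | 42 + 48 = 90 |
| Neither window applies | no limit stated | no limit stated | no limit stated |

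The last column gives the maxima when no cycle is delayed. First dose here means eribulin on day 1; lenvatinib starts on day 2. The age keeps growing by up to 24 days with each further cycle.

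**3. With a test on day 1 of each cycle**

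The age at first dose is 0 days if blood is drawn on day 1 as in footnote 3. In later cycles the 2-day draw window of 4.2 applies, so the oldest result on treatment is 24 + 2 = 26 days with no delay. This uses the same 24-day cycle as the 76 and 90 above.

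**4. Dose context**

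Section 7.2 says: "Lenvatinib is administered at a dose of 20 mg orally". Appendix I 8.1 reports fetal anomalies at doses down to 0.14 (rats) and 0.03 (rabbits) times the 24 mg human dose, scaled by body surface area.

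- Rats: 0.14 × 24 = 3.36 mg; 3.36 / 20 = 16.8% of the trial dose.
- Rabbits: 0.03 × 24 = 0.72 mg; 0.72 / 20 = 3.6% of the trial dose.

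This shows that the hazard is relevant at 20 mg. It does not indicate how often to test.

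**The case against.** The plan does address pregnancy. It has an exclusion, a baseline serum test, a signed eligibility checklist, a negative result among the run-in registration documents where applicable, history and examination every cycle, and the treating physician's discretion to stop therapy (4.7). Birth defects count as serious adverse events (9.2.3), and the SAE form has a pregnancy field. Consent pages were removed before review and may carry contraception wording. All of this stands. But none of it is a test at or after first dose, and the reporting items act only after harm. Nausea and fatigue are common with these drugs, so history alone is a weak detector.

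A reader might infer that the protocol breaks a label requirement for repeat testing. The documents do not support that: the visible label text asks for advice on fetal risk and for contraception. Testing every cycle is therefore a recommendation, and the choice of day 1 is practical.

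A reader might also take 28 and 76 days as firm limits set by the plan. They are not. The pregnancy row carries no footnote, 5.2 most naturally concerns tumour evaluation, and the gap to first dose is assumed.

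Finally, the trial is small (10 run-in and 30 phase II patients), and the note under the lenvatinib dose table in 4.3 shows that the first ten patients have already been treated. An amendment cannot help anyone already treated.

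**Conclusion.** The concern holds as a gap in scheduled testing. The strongest part is the missing test before the first dose, because the 3.1 exclusion can then rest on an old result. Under the conditional 28-day window, that result is up to 28 days old at first dose and up to 76 after two undelayed cycles. It is 42 and 90 with an assumed 14-day gap, and without stated limit if neither window applies. That a gap exists does not depend on which reading is right; only its size does.

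It would go too far to say that the plan ignores pregnancy or that an affected woman could not be taken off treatment. The documents also do not allow an estimate of how many women would be affected. This is a safety and scheduling point and changes no endpoint, alpha, power or sample-size figure. It should be made as a cheap improvement for patients still to be treated.

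**What to change.** For women of reproductive potential, a term the amendment should define:

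1. Amend the 6.0 calendar and footnote 3 to require a negative pregnancy test on the day 1 draw already scheduled for CBC and the chemistry panel, before the first dose.
2. As a recommendation beyond the visible label text, repeat the test with the day 1 draw of each later cycle.
3. Add to 4.7 that a positive test holds both drugs and that a confirmed pregnancy ends study treatment. Section 4.7 names no such rule now.

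Optionally, if the consent form does not already cover it, carry the contraception advice from Appendix I into 3.1. Its duration should follow the longer of the two drugs' labels; eribulin's is not reproduced in the documents.

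The cost is amendment wording and one assay per cycle on blood already drawn, for these women only, with no new visit. The documents give no price for the assay. The downside is an occasional false positive that briefly delays a dose.

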7.0 Drug formulation and Procurement

7.1 Eribulin

Other Names

Halaven; eribulin mesylate

Classification

Eribulin is a non-taxane, synthetic analogue of halichondrin B (a product isolated from the marine sponge *Halichondria okadai*).

Mode of Action

Eribulin is a non-taxane microtubule dynamics inhibitor. Eribulin inhibits the growth phase of microtubules without affecting the shortening phase and sequesters tubulin into nonproductive aggregates. Eribulin exerts its effects via a tubulin-based antimitotic mechanism leading to G2/M cell-cycle block, disruption of mitotic spindles, and, ultimately, apoptotic cell death after prolonged mitotic blockage.

Storage & Stability

Vials should be stored in their original cartons at 25°C (77°F); excursions are permitted to 15°-30°C (59°-86°F). Do not freeze. Undiluted Eribulin may be stored for up to 4 hours at room temperature, or for up to 24 hours under refrigeration (4°C or 40°F). Diluted solutions of Eribulin may be stored for up to 4 hours and room temperature or up to 24 hours under refrigeration. Discard unused portions of the vial.

Protocol Dose

Eribulin will be given at a dose of 1.4 mg/m² administered intravenously over 2-5 minutes.

Preparation

Eribulin will be supplied in commercially-labeled vials as a clear, colorless, sterile solution for intravenous administration. Each vial contains 1 mg of Eribulin mesylate as a 0.5 mg/ml solution in ethanol: water (5:95). Eribulin should be administered undiluted or diluted in 100 mL of 0.9% sodium chloride injection, USP.

Protocol Administration

Eribulin will be administered via intravenous infusion over 2-5 minutes. Treatments will be administered on cycle days 1 and 8.

Incompatibilities

Eribulin should not be diluted in, or administered through, an intravenous line containing solutions with dextrose.

Availability

Eribulin will be supplied by Eisai, Inc in vials labeled for clinical use containing 1 mg/2mL Eribulin mesylate as a 0.5 mg/ml solution in ethanol: water (5:95). To order drug, please contact EISAI IIS Department at [contact] or [contact]

Side Effects

Detailed information regarding side effects and rates of adverse events of Eribulin can be found in the package insert. Some of the most common side effects include:

Hematologic: The most common hematologic toxicities (occurring in $\geq 25\%$ of patients) are neutropenia and anemia. The most common serious adverse events were febrile neutropenia (4%) and neutropenia (2%).

Gastrointestinal: Most common are nausea and constipation (occurring in $\geq 25\%$ of patients). Other GI adverse events include diarrhea and vomiting.

Neurologic: Peripheral neuropathy (incidence of $\geq 25\%$) is the most common.

Other: Asthenia/fatigue and alopecia are the most common (occurring in $\geq 25\%$ of patients) miscellaneous adverse events.

Nursing Implications

Monitor CBC and platelet counts.

Monitor for signs of neuropathy.

Monitor for prolonged QT intervals in patients with congestive heart failure, bradyarrhythmias, drugs known to prolong the QT interval, and electrolyte abnormalities.

